5.4.3.3. Electrocardiogram

5.4.3.3.1. Definition of ECG variables

5.4.3.3.1.1. ECG parameter measurements

The following variables are collected: Heart Rate (HR) (bpm), PR interval (ms), QRS (ms), QT (ms). Corrected QT values QTcF (ms) and QTcB (ms) (based on Fridericia's and Bazett's formulae) are provided by the central vendor and will not be recalculated.

Data are stored along with nominal visit and time point labels that will be used for the analysis. Extension/core baseline is flagged and absolute and percent changes from baseline are calculated for each post-baseline value. In the same manner, pre-dose values are flagged and absolute and percent changes from pre-dose are calculated for the hourly post-dose assessments after first dose on extension study Day 1 at re-initiations during the extension study.

For by-visit and by-hour tables presenting summary statistics of quantitative ECG results, the latest (by date/time) transmitted measurement per nominal subject-visit / time point is used in case of multiple data available at that visit or visit / time point.

Assessments meeting the following conditions for **notable abnormalities** are flagged in the ADaM dataset:

- Heart rate ≤ 50 bpm;
- Heart rate ≤ 45 bpm;
- Heart rate ≤ 40 bpm;
- PR interval > 200 ms and increase of > 20 ms compared to baseline assessment;
- QTcF/QTcB prolongation of > 500 ms;
- QTcF/QTcB prolongation of > 480 ms;
- QTcF/QTcB prolongation of > 450 ms;
- QTcF/QTcB increase from baseline of > 30 ms;
- OTcF/OTcB increase from baseline of > 60 ms;
- QTcF/QTcB prolongations of > 500 ms and increase from baseline of > 30 ms;
- QTcF/QTcB prolongations of > 500 ms and increase from baseline of > 60 ms;
- QTcF/QTcB prolongations of > 450 ms and increase from baseline of > 30 ms;
- QTcF/QTcB prolongations of > 450 ms and increase from baseline of > 60 ms.

Notable abnormalities are derived for the Extension Analysis Period using extension baseline as a reference, and additionally for the Combined Analysis Period using the core baseline as a reference.

In addition, assessments meeting the following conditions for notable abnormalities on Day 1 of re-initiation during the Extension Analysis Period are flagged in the ADaM dataset:

- PR interval > 200 ms and increase of > 20 ms compared to pre-dose assessment;
- OTcF/OTcB increase from pre-dose of > 30 ms;

• QTcF/QTcB increase from pre-dose of > 60 ms.

For details of the ECG notable abnormality flags derived during the core study. These variables are used as derived in the core study and are not re-derived for the extension analysis.

For presentation of these outliers in by-visit and by-hour tables, the most extreme (i.e., lowest heart rate and highest interval) is considered in case of multiple data available at that visit or visit / time point.

5.4.3.3.1.2. Morphological ECG findings

Morphological ECG findings are reported by the central reader, and mapped to CDISC standard (codelist C71153, with high level categories from codelist C71152) in the SDTM.

For details of the morphological ECG findings variables collected during the core study, see the core SAP [D-19.178]. These variables are used as derived in the core study, and are not re-derived for the extension analysis.

For analyses in tables the following categories are anticipated:

- Atrioventricular Conduction
- Axis and Voltage
- Chamber Hypertrophy or Enlargement
- Conduction
- Ectopy
- Intraventricular-Intraatrial Conduction
- Rhythm Not Otherwise Specified
- ST Segment, T wave, and U wave
- Sinus Node Rhythms and Arrhythmias
- Supraventricular Arrhythmias
- Supraventricular Tachyarrhythmias
- Ventricular Arrhythmias

Findings related to interpretation or technical issues are only included in listings.

Morphological ECG findings are flagged as "New" if not present at any assessment prior to first treatment in the Analysis Period, or "Pre-existing" if present at such assessment. For the Combined Analysis Period, in case of missing or non-evaluable pre-treatment ECG assessment, it is conservatively assumed that any treatment-emergent morphological ECG finding is "New".

Morphological ECG findings on Day 1 of (any) re-initiation

Morphological ECG findings on Day 1 of a re-initiation are those findings that start at or after the time of the ponesimod administration on Day 1 of a re-initiation, and before the following calendar date.

Morphological ECG findings with onset on Day 1 of re-initiation are considered with respect to any re-initiation of ponesimod during the Extension Analysis Period. Morphological ECG findings on Day 1 of a re-initiation are considered to be "New" if they were not present at any pre-dose assessment on the day of re-initiation, or if no pre-dose assessment on day of re-initiation was performed.

For presentation of these findings in by-visit and by-hour tables, all reported abnormalities are considered in case of multiple assessments available at that visit or visit / time point.

5.4.3.3.2. Analysis of ECG

The following outputs will be produced for ECG, both for the Combined Analysis Period, by core study treatment, using SAF (the summaries marked with § will include only the subjects who were initially treated with ponesimod 20 mg in the core study), and for the Extension Analysis Period, by core study treatment and overall, using the EXTS:

- Summary of absolute values for ECG parameters (HR, PR, QRS, QT, and QTcF / QTcB): descriptive statistics by visit;
- Summary of absolute and absolute change from baseline values for ECG parameters (HR, PR, QRS, QT, and QTcF / QTcB): descriptive statistics by visit. Mean changes from baseline in heart rate are also presented graphically with their standard error over time (plots starting with zero change at baseline);
- Incidence of treatment-emergent notable abnormalities (PR prolongations and HR outliers as defined in Section 5.4.3.3.1.1): frequency counts and percentages, overall and by visit, where percentages are based on the number of subjects with at least one post-baseline value (i.e., number of subjects at risk);§
- Incidence of clinically relevant morphological ECG findings [as defined in Section 5.4.3.3.1.1], by abnormality and group term, overall and by visit: frequency counts and percentages;§

The following outputs will be produced for the Extension Analysis Period only, by core study treatment and overall, using the EXTS:

- Summary of pre- and post-dose values for ECG parameters (HR, PR, QRS, QT, and QTcF / QTcB) on Day 1 of first re-initiation: descriptive statistics time point. Strictly speaking the Day 1 of extension study is also counted as "Day 1 of first re-initiation" as subjects had experienced study treatment interruption between end of core study and start of extension study. Nevertheless in this context the "Day 1 of first re-initiation" applies for re-initiation after a study drug interruption during extension period.
- Summary of absolute and absolute change from pre-dose values for post-dose values of ECG parameters (HR, PR, QRS, QT and QTcF / QTcB) on Day 1 of first re-initiation: descriptive statistics by time point.
- Incidence of treatment-emergent PR prolongations and HR outliers [as defined in Section 5.4.3.3.1.1] on Day 1 of (any) re-initiation: frequency counts and percentages, overall post-dose and by post-dose time point, where percentages are based on the number of subjects with at least one post-dose value (i.e., number of subjects at risk).
- Incidence of clinically relevant morphological ECG findings on Day 1 of (any) re-initiation by abnormality and group term, overall and by time point: frequency counts and percentages.

Only newly occurring treatment-emergent abnormalities and findings are reported, i.e. if a subject has a particular event/finding prior to first treatment in the Analysis Period, and the same event/finding occurs again during the Analysis Period, it will not be reported in the summary table. "Pre-existing" findings will be only flagged in datasets and reported in listing. Unscheduled visits are not presented in summary tables by visit. Unscheduled assessments that meet the pre-defined high/low criteria will be flagged and may be included in the corresponding incidence tables.

All ECG notable abnormality data as specified above will be included in listings.

5.4.3.4. Spirometry and DLco

5.4.3.4.1. Definition of Spirometry and DLco

Spirometry tests are performed to assess pulmonary function.

In the core study, spirometry measurement data are collected using vendor machines from ERT and data are automatically submitted to ERT by the machine. In the extension study, spirometry measurement data are assessed at site and entered on the eCRF.

The following variables are collected in the extension study:

- FEV₁ (Forced Expiratory Volume in 1 Second) [L];
- FVC (Forced Vital Capacity) [L];

The following variables are derived for analysis (predicted values based on Quanjer [Quanjer 1993]):

- FEV_1 / FVC ratio = $FEV_1 [L] / FVC [L]$;
- Predicted normal FEV₁[L] for male subjects = $4.30 \times \text{height (m)} 0.029 \times \text{age (years)}$ at extension study enrollment -2.49;
- Predicted normal FEV₁[L] for female subjects = $3.95 \times \text{height (m)} 0.025 \times \text{age (years)}$ at extension study enrollment -2.60;
- Predicted normal FVC[L] for male subjects = $5.76 \times \text{height (m)} 0.026 \times \text{age (years)}$ at extension study enrollment 4.34;
- Predicted normal FVC[L] for female subjects = $4.43 \times \text{height (m)} 0.026 \times \text{age (years)}$ at extension study enrollment -2.89.

For the predicted normal values derivations above, age as collected at study extension enrollment and height collected at core study screening are used; also *age* is set to 25 years if age is between 18 and 25 years and a conversion factor of 0.9 must be multiplied to the predicted normal value if subject race is other than 'White'.

• Percent of the corresponding predicted normal value is also calculated for FEV₁[L] and FVC[L] as follows:

Percent of the predicted value (%) = [measured value] $\times 100$ / [predicted normal value]

The percent of the predicted normal values FEV_1 and FVC, as calculated by the vendor, for core study data will be used, and are not re-derived for the extension analysis.

For the core study assessments, analyses are based on best efforts, for details see CSR SAP for core study.

Core/extension baseline is flagged and absolute and percent changes from core/extension baseline are calculated for each post-baseline value.

Assessments meeting the following conditions are flagged in the ADaM dataset:

- Percent change from baseline in FEV₁: <-20%, <-30%;
- Percent change from baseline in FVC: < -20\%, < -30\%;
- Absolute change from baseline in %PRED FEV₁: < -20%, < -30%;

- Absolute change from baseline in %PRED FVC: < -20%, < -30%;
- $FEV_1/FVC < 70\%$.

For details of the same conditions for the core study, see the core SAP. These flags are used as derived in the core study, and are not re-derived for the extension analysis.

Spirometry - DL_{CO}

Subjects who participated in the DL_{CO} sub-study during the core study were asked to continue their participation in the DL_{CO} sub-study during the extension study. Subjects who chose to continue participation provided consent under a separate informed consent for the DL_{CO} sub-study.

The DL_{CO} assessment is conducted at extension study Visits 3, 7, 11, 15, 19, EOT, and EOS. In addition, unscheduled DL_{CO} tests may be performed at any time during the study.

An assessment usually consists of multiple maneuvers. Among multiple maneuvers (reported within the same visit and assessment date), the mean value of the two highest DL_{CO} measurements are derived to represent the DL_{CO} at that assessment. If only one DL_{CO} measurement is available at an assessment, that measurement is used. Within the eCRF, DL_{CO} values are converted into 'mmol/min/kPA', which is the unit used in reporting.

Only these derived assessment-level values are used for any further derivations, the term ' DL_{CO} at visit' will refer to this value derived from the individual maneuvers measurements.

The following derivations are performed for DL_{CO} from all measurements:

- DL_{CO} adjusted for Hemoglobin (Hb) is derived based on the method of Cotes [Macintyre 2005]
 using the Hb reported by the central laboratory (or from local laboratory if missing) at the same
 nominal visit based on below formulae:
 - DL_{CO Hb corrected} = DL_{CO} × $(10.22 + \text{Hb [g/dL]}) / (1.7 \times \text{Hb [g/dL]})$ for male subjects older than 14 years;
 - DL_{CO Hb corrected} = DL_{CO} × (9.38 + Hb [g/dL]) / $(1.7 \times \text{Hb [g/dL]})$ for female subject subjects and all subjects ≤ 14 years;

If no Hb value is available at the corresponding visit, this variable is missing.

- Predicted DL_{CO} corresponding to each assessment is derived based on Cotes [Cotes 1993] as follows:
 - DL_{CO predicted} = $11.11 \times \text{Height [m]} 0.066 \times \text{Age [years]} 6.03$, for male subjects, age is set to 25 years if age below 25 years;
 - DL_{CO predicted} = $8.18 \times \text{Height [m]} 0.049 \times \text{Age [years]} 2.74$, for female subjects, age is set to 25 years if age below 25 years;

The age used in above formula is derived as follows: Age at baseline +0.5 + (Date of assessment - Date of (re-)screening) / 365.25;

 Percent Predicted DL_{CO} is derived as: 100 × DL_{CO} Hb corrected / DL_{CO} predicted

Assessments meeting the following conditions **for notable abnormality** are flagged in the ADaM dataset:

- Percent change from baseline in DL_{CO}: < -20%;
- Percent change from baseline in hemoglobin corrected $DL_{CO d}$: <-20%;
- Absolute change from baseline in Percent predicted DL_{CO} : < -20%.

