5.1.3. Baseline and change-from-baseline

5.1.3.1. Extension Baseline

The **extension baseline value** for efficacy and safety is the last valid non-missing assessment that is taken on or after EOT visit in the core study, and prior to first study drug intake in the extension study. Records meeting these criteria in both core or the extension database are considered for extension baseline. Consequently, the extension baseline value may be the pre-dose assessment on Day 1 of the extension study, but it may also be the value at any visit from EOT visit of the core study (EOT/FU1/FU2 or unscheduled visits). In particular, laboratory parameters are not scheduled to be assessed on Day 1 of the extension study, and so (unless there is an eligible unscheduled assessment) the extension baseline for laboratory parameters will be the last value as above observed in the core study.

Specifically, for MRI and PFT variables only, in case of available assessments on extension Day 1, these should be considered as valid assessments for the extension baseline derivation, even if taken after first dose of treatment on Day 1.

In case of multiple ECG or vital signs assessments (for the same subject, visit, parameter) in the core study visits (EOT/FU1/FU2 or unscheduled visits) that should be considered for the purpose of the baseline value derivation, the average of the results should be taken for use as baseline record.

The derived "extension baseline" value is considered a visit and is displayed in the Combined Analysis Period by visit tables, with corresponding change from core baseline to "extension baseline".

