5.1.3.2. Core Baseline

The **core baseline value** for efficacy is defined as the last non-missing value recorded before or on randomization in the core study for each endpoint and each subject individually.

The **core baseline value** for safety is defined as the last non-missing value recorded before the first study treatment administration in the core study for each endpoint and each subject individually.

These variables are used as derived in the core study and are not re-derived for the extension analysis.

On days where study drug is initiated or re-initiated, the pre-dose assessment for that day is defined as the last non-missing assessment prior to the study drug intake on that day. The pre-dose assessment on Day 1 of the Analysis Period (if available) is identical to the corresponding baseline for that Analysis Period. In case of (partially) missing assessment dates/times, or for assessments reported on Day 1 (or day of re-initiation) with recorded assessment time contradicting the time point label (e.g., pre-dose, 2 hours post-dose), the nominal visit and time point labels will be used to determine whether an assessment is considered for baseline (e.g., a blood pressure measurement with an assessment date on Day 1 but with a missing assessment time or an assessment time prior to the reported time of first study drug intake will not be considered for baseline if reported under the time point "2 hours post-dose" in the eCRF; however, it will be considered if reported as "Predose" in the eCRF).

Analysis over the Extension Analysis Period will use the **extension study baseline**, while analysis over the Combined Analysis Period will use the **core study baseline**.

Absolute change from baseline is defined as post-baseline value minus baseline value, i.e., a positive sign indicates an increase compared to baseline. A percentage change from baseline is defined as the absolute change from baseline divided by the baseline value (if the baseline value is > 0) and then multiplied by 100. Absolute and percent change from both core and extension baseline is calculated and stored for all continuous safety data.

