5.1.6. Definition of treatment-emergent

A safety assessment (ECG, vital signs, laboratory, etc.) is considered treatment-emergent relative to the Analysis Period, and a safety event (AE, serious adverse event [SAE], Death, etc.) is considered treatment-emergent relative to the Analysis Period, if the assessment date is on or after the study treatment start date in the Analysis Period and prior to or on the study treatment end date + 15 days (inclusive). In case of planned pregnancy interruption, a safety assessment is considered treatment emergent relative to the Analysis Period if one of the following conditions is met:

- the assessment date is on or after the study treatment start date in the Analysis Period and prior to or on the last study drug intake date prior to pregnancy interruption + 15 days (inclusive)
- the assessment date is on or after the re-initiation date of study treatment after planned pregnancy and prior to or on the End of Treatment (EOT) date + 15 days (inclusive).

In case of multiple planned pregnancies interruptions, the above definition will be adapted, that any assessment in the following interval is not considered as treatment emergent: date between the last study drug intake date prior to each pregnancy interruption + 15 days (inclusive) and the reinitiation date of study treatment after each planned pregnancy (excluded).

If both the assessment date/time and the date/time of study treatment start (or of re initiation after planned pregnancy) are available, only events with date/time on or after the date/time of study treatment start (or of re initiation after planned pregnancy) are considered to be treatment emergent. In case of (partially) missing assessment dates/times, or for assessments on treatment Day 1 with reported assessment time contradicting the time point label, the nominal visit and time point labels will be used to determine whether an assessment is considered as treatment-emergent or not. For example, a blood pressure measurement with an assessment date on Day 1 but a missing assessment time or an assessment time after the time of first study drug intake, will not be considered treatment emergent if reported under the time point "Pre-dose" in the eCRF, however it will be considered treatment-emergent if reported as "2 hours post-dose" in the eCRF.

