- 2) Visit 1 includes a pre-treatment period which lasts from signing of the informed consent until first dosing of study treatment. Ideally, all assessments and procedures of Visit 1 (e.g., signing of the informed consent, first study treatment dosing and post-dose cardiac monitoring) should occur on the same day as the core study FU1 or abbreviated FU2 (whichever applies). In all cases, informed consent should be signed no later than one day after FU1 or FU2 visit (whichever applies) and all assessments and procedures of Visit 1 must be completed (i.e., study treatment start) no longer than 7 days after signing of the informed consent. The date of Day 1 corresponds to the date of the first dose of study treatment in the extension study. The investigator should make every effort to minimize the duration between EOT of the core study and Day 1 of the extension study. Ideally the treatment interruption should last no longer than 15 days.
- 3) At every study visit, subjects are reminded to contact their principal investigator / treating neurologist at the clinical site immediately in the event of the appearance of any new or worsening neurological symptoms. In addition, the site will contact the subject 6 weeks (± 7 days) after each visit starting with Visit 4 (Week 12) in order to proactively inquire about any new or worsened neurological symptoms. Whenever, between visits, a subject experiences any new or worsening neurological symptoms, he/she must contact the principal investigator / treating neurologist, study nurse or clinical coordinator as soon as possible in order to complete a relapse assessment questionnaire [see protocol appendix 10].
- 4) Dermatological examination to be performed by a dermatologist.
- 5) Systolic / diastolic blood pressure: Only pre-dose except Day 1. On Day 1 pre-dose and hourly (± 15 min) for at least 4 hours post-dose and up to 12 hours.
- 6) ECGs: Only pre-dose except Day 1. On Day 1 pre-dose and hourly (± 15 min) for at least 4 hours post-dose and up to 12 hours.
- 7) OCT and/or ophthalmological examination to be performed at any visit in the presence of visual symptoms suggestive of macular edema or active uveitis.
- 8) PFTs including spirometry to be performed in all subjects; DL_{CO} to be performed in a subset of subjects at selected sites only.
- 9) Monitoring of hematology/chemistry every 4 weeks for the first 24 weeks after enrollment (±7 days).

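### Percent-predicted FEV1 and FVC drift downwards over the extension because age is held at its enrollment value

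*SAP*

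**What the plan says.** **Age.** Section 5.4.3.4.1 gives equations for predicted FEV1 and FVC and states that "age as collected at study extension enrollment and height collected at core study screening are used". For predicted DLco the same section has a different rule: "The age used in above formula is derived as follows: Age at baseline +0.5 + (Date of assessment", with the time since (re-)screening added. Section 5.4.3.1.1 likewise recalculates age at each assessment for creatinine clearance.

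**Source of percent predicted.** Core-study values are those "as calculated by the vendor, for core study data will be used, and are not re-derived for the extension analysis". Extension spirometry is measured at site, entered on the eCRF and converted with the SAP equations, including a factor of 0.9 for subjects whose race is not White.

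**Extension baseline.** Section 5.1.3.1 requires a value taken "prior to first study drug intake in the extension study", then accepts a Day 1 MRI or lung function test "even if taken after first dose of treatment on Day 1".

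**Endpoints.** Table 2 lists falls of more than 20 percentage points in percent-predicted FEV1 and FVC, and separately falls of more than 20% and 30% in FEV1 or FVC themselves.

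**The concern.** A percent-predicted value is meant to remove the loss of lung function expected with age. If age, height and race factor are all fixed at enrollment, the denominator is a constant for each subject. Percent predicted within the extension is then the litre value rescaled, and the age adjustment is lost. Ordinary ageing accumulates as apparent decline, always in the same direction, in every by-visit percent-predicted mean and plot and in the 20-point flag. The study is non-comparative, so no concurrent control arm would show how much of the fall is artefact. The SAP gives no reason for treating spirometry differently from DLco.

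Two further matters bear on the change from baseline. A change from a core-visit baseline to an extension visit crosses from the vendor's calculation to the SAP's. And a lung function test taken after the first extension dose can become the reference value, although bronchoconstriction is a pre-defined adverse event of special interest (Section 5.4.2.2.10).

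**Working it through.** The SAP states no figure for this effect, so there is none to reproduce.

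**1. Frozen age.** Inputs from the SAP: the four prediction equations (Section 5.4.3.4.1), 240 weeks of treatment (Section 1.2.3) and 288 weeks in Ukraine (Section 1.2.3.1). Assumptions: heights 1.70 to 1.86 m for men and 1.57 to 1.73 m for women, ages 30 to 55, and a subject who stays at 95% of the value predicted for the current age.

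Elapsed time: 240 × 7 / 365.25 = 4.60 years; 288 × 7 / 365.25 = 5.52 years; 48 × 7 / 365.25 = 0.92 years.

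Spurious change in points = 95 × [pred(age + t) / pred(age) − 1].

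Example, man aged 40, 1.78 m, FEV1: 4.30 × 1.78 − 0.029 × 40 − 2.49 = 4.004 L at enrollment; 4.004 − 0.029 × 4.60 = 3.871 L at Week 240; 95 × (3.871 / 4.004 − 1) = −3.2 points.

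| Age 40 at enrollment | Predicted at enrollment (L) | Predicted at Week 240 (L) | Spurious change (points) |
|---|---|---|---|
| Man 1.78 m, FEV1 | 4.004 | 3.871 | −3.2 |
| Woman 1.65 m, FEV1 | 2.917 | 2.803 | −3.7 |
| Man 1.78 m, FVC | 4.873 | 4.753 | −2.3 |
| Woman 1.65 m, FVC | 3.379 | 3.260 | −3.4 |

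Over the whole grid of heights and ages the range is −0.4 to −1.0 at Week 48, −2.0 to −4.9 at Week 240 and −2.4 to −5.9 at Week 288. With age updated at each assessment the change is zero by construction.

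Effect on the flag at one late visit, from a normal model with assumed SD and true mean change, for a shift of −3 to −4 points:

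| Assumed SD, mean | Share below −20, no shift | With shift |
|---|---|---|
| 8, 0 | 0.6% | 1.7% to 2.3% |
| 10, −2 | 3.6% | 6.7% to 8.1% |
| 12, −2 | 6.7% | 10.6% to 12.2% |

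**2. Two derivations.** The SAP does not give the vendor's equation, age basis or race factor, so only scenarios are possible, again at 95% of predicted.
- All identical: no step.
- Vendor used an age 2.2 years younger (38 against 40.2): 95 × [pred(38) / pred(40.2) − 1] = +1.5 points (man, 1.78 m) and +1.8 points (woman, 1.65 m) in FEV1. This is upward, against the drift in step 1.
- Vendor used no 0.9 factor: a non-White subject would move from 95% to 95 / 0.9 = 105.6%.

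**3. Post-dose baseline.** Passages side by side:
- The general rule in Section 5.1.3.1 is pre-dose; the exception for lung function tests is not.
- Section 5.1.3.2 says: "The pre-dose assessment on Day 1 of the Analysis Period (if available) is identical to the corresponding baseline for that Analysis Period". If a later post-dose test on Day 1 is taken as the last valid value, that cannot hold.
- Section 5.1.6 counts as treatment-emergent "only events with date/time on or after the date/time of study treatment start", so a post-dose Day 1 test would be both baseline and treatment-emergent.
- Table 12 in Appendix 12 schedules lung function tests at FU1 and none on Day 1, but Visit 1 procedures ideally "should occur on the same day as the core study FU1 or abbreviated FU2", so the exception can apply.

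If the first dose lowers FEV1 by a fraction d (assumed), the fall from the pre-dose value needed to reach the 20% flag is 1 − (1 − d) × 0.8: 21.6% for d = 2%, 24.0% for 5%, 28.0% for 10%.

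**The case against.** A reader might infer that the spirometry safety endpoints as a whole are distorted. They are not. FEV1 and FVC in litres, their percent change, the 20% and 30% flags on them, and FEV1/FVC use no predicted value, so neither the frozen age nor the mixed derivation can reach them. Litre changes are tabulated alongside (Section 5.4.3.4.2), which gives a careful reader a check. All this stands and limits the point to percent predicted.

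The drift is largest at the end. It is about one point or less at Week 48, and subjects whose country gains commercial supply stop earlier. The analyses are exploratory with no hypotheses (Section 2), and the error overstates harm rather than hiding it. This bears on priority, but does not justify an age rule that contradicts the one for DLco in the same section.

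Keeping core variables as derived is this SAP's general convention, and the vendor's equation may be the same. That stands: the step may be nil. A subject whose baseline is a Day 1 test in the extension eCRF has no such step in the change from extension baseline.

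The post-dose rule is an explicit exception, not an oversight. A Day 1 test may often be the same-day FU1 test itself, so there may be no separate FU1 value to displace, and a strict pre-dose rule could leave a subject without a baseline. This too stands, and the fix allows for it.

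**Conclusion.** The frozen age biases percent-predicted FEV1 and FVC towards decline by about 2 to 5 points at Week 240, roughly one tenth to one quarter of the 20-point threshold. The direction follows from the equations. The size rests on the assumed heights, ages and 95% level, and on normal ageing following the equations' own slope. The flag rates also rest on assumed SDs and means and are illustrative only.

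It would be tempting to say that the mixed derivation creates further decline. The SAP does not support this: neither size nor direction can be determined from it, and one plausible scenario runs upward.

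It would also be tempting to say that the post-dose baseline hides real decline across the study. The internal contradiction is real, but it affects only the Extension Analysis Period and subjects with a post-dose Day 1 test. Their number is not stated and is probably small, and the size of any acute dose effect is an assumption. It runs opposite to the age drift but in different subjects and partly different endpoints, so the two cannot be relied on to cancel.

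The age rule should be corrected. The other two are secondary.

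**What to change.** 1. Compute predicted FEV1 and FVC with age at each assessment, using the rule already written for DLco. This is a one-line derivation change on data already held.
2. For the change-from-baseline analyses, derive percent predicted for core-visit baselines with the same equations, keeping any core follow-up visits compared with them on the same scale. Alternatively, confirm in the SAP that the vendor's equation, age basis and race factor are identical. Differences between vendor machines and site equipment would remain either way.
3. For the Extension Analysis Period, use a pre-dose test (core EOT, FU1, unscheduled or pre-dose Day 1) as baseline wherever one exists. If only a post-dose Day 1 test exists, keep it, flag it, and add a sensitivity table without such subjects. The MRI exception can stay.

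Cost: SAP wording, reprogramming and one extra table, with no new data. Some core percent-predicted values and flags, which the SAP now keeps as derived, may differ slightly from the core report; a footnote should say so.
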